##### **8.4.10.1. Neutropenia**

###### **8.4.10.1.1. During Treatment (Period 2)**

**During treatment with investigational product**, patients with neutrophil counts  $< 1500$  cells/ $\mu$ L ( $< 1.50 \times 10^3$ / $\mu$ L or  $< 1.50$  GI/L) are to be managed for neutropenia as follows:

- $< 500$  cells/ $\mu$ L ( $< 0.50 \times 10^3$ / $\mu$ L or  $< 0.50$  GI/L), see Discontinuation Criteria (Section [7.1](#))
- $\geq 500$  cells/ $\mu$ L and  $< 1000$  cells/ $\mu$ L ( $\geq 0.50 \times 10^3$ / $\mu$ L and  $< 1.00 \times 10^3$ / $\mu$ L or  $\geq 0.50$  GI/L and  $< 1.00$  GI/L), see Discontinuation Criteria (Section [7.1](#))
- $\geq 1000$  cells/ $\mu$ L and  $< 1500$  cells/ $\mu$ L ( $\geq 1.00 \times 10^3$ / $\mu$ L and  $< 1.50 \times 10^3$ / $\mu$ L or  $\geq 1.00$  GI/L and  $< 1.50$  GI/L), and the patient has a concurrent infection that requires systemic anti-infective therapy (for example, antibiotic, antifungal agent, antiviral agent):

- The dose of investigational product is to be withheld, the patient is to receive appropriate medical care, and a repeat test for neutrophil count is to be performed within 4 weeks from knowledge of the initial report. If the repeat neutrophil count has returned to  $\geq 1500$  cells/ $\mu\text{L}$  ( $\geq 1.50 \times 10^3/\mu\text{L}$  or  $\geq 1.50 \times 10^3/\mu\text{L}$ ) and the infection has resolved or is resolving, the patient may resume dosing of investigational product and evaluation at scheduled visits. If the neutrophil count remains  $\geq 1000$  cells/ $\mu\text{L}$  and  $< 1500$  cells/ $\mu\text{L}$  ( $\geq 1.00 \times 10^3/\mu\text{L}$  and  $< 1.50 \times 10^3/\mu\text{L}$  or  $\geq 1.00$  GI/L and  $< 1.50$  GI/L), investigational product is to continue to be withheld and a repeat neutrophil count is to again be performed within another 4 weeks. If, after 2 repeat tests, the neutrophil count still remains  $\geq 1000$  cells/ $\mu\text{L}$  and  $< 1500$  cells/ $\mu\text{L}$  ( $\geq 1.00 \times 10^3/\mu\text{L}$  and  $< 1.50 \times 10^3/\mu\text{L}$  or  $\geq 1.00$  GI/L and  $< 1.50$  GI/L), and:
  - the infection has not fully resolved; the patient will be discontinued from the study treatment.
  - the infection has resolved; the patient may resume dosing and evaluation at scheduled visits. However, if resumption of dosing is not deemed appropriate by the investigator, the patient will be discontinued from the study treatment.
- $\geq 1000$  cells/ $\mu\text{L}$  and  $< 1500$  cells/ $\mu\text{L}$  ( $\geq 1.00 \times 10^3/\mu\text{L}$  and  $< 1.50 \times 10^3/\mu\text{L}$  or  $\geq 1.00$  GI/L and  $< 1.50$  GI/L), and the patient has no concurrent infection that requires systemic anti-infective therapy (for example, antibiotic, antifungal agent, antiviral agent):
  - Dosing may continue, and a repeat neutrophil count is to be performed 4 to 8 weeks from knowledge of the initial report. Testing may be at a regularly scheduled visit or at an unscheduled visit, as necessary.

Repeat testing is to be performed at 4- to 8-week intervals until the neutrophil count has returned to  $\geq 1500$  cells/ $\mu\text{L}$  ( $\geq 1.50 \times 10^3/\mu\text{L}$  or  $\geq 1.50$  GI/L). If the patient has 3 or more postbaseline neutrophil counts of  $\geq 1000$  cells/ $\mu\text{L}$  ( $\geq 1.00 \times 10^3/\mu\text{L}$  or  $\geq 1.00$  GI/L) and  $< 1500$  cells/ $\mu\text{L}$  ( $< 1.50 \times 10^3/\mu\text{L}$  or  $< 1.50$  GI/L), no value of  $< 1000$  cells/ $\mu\text{L}$  ( $< 1.00 \times 10^3/\mu\text{L}$  or  $< 1.00$  GI/L), and no postbaseline infection requiring systemic anti-infective therapy, the patient may continue or resume further evaluation at scheduled visits, as deemed appropriate by the investigator.

If a patient without initial concurrent infection develops an infection that requires systemic anti-infective therapy, then the patient is to be managed as indicated above for patients with concurrent infection.

#### **8.4.10.1.2. At Early Termination Visit**

*For patients not enrolling in Study RHBX:* If, at the last scheduled study visit, the patient's neutrophil count is  $< 1500$  cells/ $\mu\text{L}$  ( $< 1.50 \times 10^3/\mu\text{L}$  or  $< 1.50$  GI/L) and less than the patient's baseline neutrophil count, the following measures are to be taken:

- *Patients with Concurrent Infection:* If there is a concurrent infection that requires systemic anti-infective therapy, the patient must receive appropriate medical care and a repeat test for neutrophil count is to be performed at least Q4W (or sooner as appropriate) until resolution of infection. Upon resolution of infection, the neutrophil count is to be monitored using the required study visits in the Post-Study Follow-Up Period (Period 3) design at Visits 801 (4 weeks post-resolution of infection), 802 (8 weeks after Visit 801 unless otherwise specified), and 803 (if necessary; 12 weeks after Visit 802); additional visits may be required depending on the degree of neutropenia. For patients with a neutrophil count below the above mentioned threshold at Week 52 who have already enrolled in Study RHBX, requirements for repeat test for neutrophil count will be specified in the Study RHBX protocol.
- *Patients without Concurrent Infection:* If there is no concurrent infection that requires systemic anti-infective therapy, the neutrophil count is to be monitored using the required study visits in the Post-Study Follow-Up Period (Period 3) design, Visits 801 (4 weeks post-ETV or last regularly scheduled visit), 802, and 803 (if necessary); additional visits may be required depending on the degree of neutropenia.

#### **8.4.10.1.3. Post-Study Follow-Up**

For patients not enrolling in Study RHBX, at Visit 801 and subsequent visits, the following monitoring applies:

- As long as a patient's neutrophil count is  $<1000$  cells/ $\mu\text{L}$  ( $<1.00 \times 10^3/\mu\text{L}$  or  $<1.00$  GI/L) at any follow-up visit, the patient is to return for visits at least Q4W (may require unscheduled visits).
- As long as a patient's neutrophil count is  $\geq 1000$  cells/ $\mu\text{L}$  and  $<1500$  cells/ $\mu\text{L}$  ( $\geq 1.00 \times 10^3/\mu\text{L}$  and  $<1.50 \times 10^3/\mu\text{L}$  or  $\geq 1.00$  GI/L and  $<1.50$  GI/L) at any follow-up visit, the patient is to return for additional visit(s) at least every 4 to 8 weeks (may require unscheduled visits).
- If, at Visit 802 or Visit 803, the patient's neutrophil count is  $\geq 1500$  cells/ $\mu\text{L}$  ( $\geq 1.50 \times 10^3/\mu\text{L}$  or  $\geq 1.50$  GI/L) or greater than or equal to the patient's baseline neutrophil count (whichever is lower), the patient's participation in the study will be considered complete unless the investigator deems additional follow-up may be necessary.

If, at Visit 803, the patient's neutrophil count remains  $<1500$  cells/ $\mu\text{L}$  ( $<1.50 \times 10^3/\mu\text{L}$  or  $<1.50$  GI/L) and less than the patient's baseline neutrophil count, or if the investigator deems additional follow-up may be necessary, the investigator in consultation with Lilly, or qualified designee, will determine the appropriate management of the patient and the appropriate timing of additional contact(s) or visit(s).

#### **8.4.10.2. Hepatitis B Monitoring**

Patients who are HBcAb+ at screening, regardless of other hepatitis B testing results, will have a serum HBV DNA specimen obtained to be analyzed by the central laboratory. Such patients

who are determined to be HBV DNA negative (undetectable) may be enrolled into the study with required HBV DNA monitoring every 3 to 4 months during treatment and 12 weeks after the last dose of ixekizumab. Patients who are found to be HBV DNA positive (detectable) at screening will be excluded from the trial.

If the result of any subsequent HBV DNA testing is positive, the patient is to be discontinued from the study treatment, is to continue safety follow-up, and is to receive appropriate follow-up medical care, including consideration for antiviral therapy. A specialist physician in the care of patients with hepatitis (for example, infectious disease or hepatologist subspecialists) should be consulted and potentially start antiviral therapy prior to discontinuation of any immunosuppressant therapy (including investigational drug). Timing of discontinuation from the study treatment and of any immunosuppressant therapy/immunomodulatory therapy (including investigational product) needs to be based on the recommendations of the consulting specialist physician in conjunction with the investigator and medical guidelines/standard of care.

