### Diagnosics Assessments

- [38] Have a body temperature  $\geq 38^{\circ}\text{C}$  ( $100.5^{\circ}\text{F}$ ) at baseline randomization
- Note:** These patients may be rescreened once  $\geq 4$  weeks after documented resolution of elevated temperature.
- [39] Have evidence or suspicion of active or latent TB (refer to Section 5.3 for rescreening and Section 8.4.6 for details on determining full TB exclusion criteria)

[40] Are positive for human immunodeficiency virus (HIV) serology; ie, positive for human immunodeficiency virus antibody (HIVAb)

[41] Have evidence of or test positive for hepatitis B virus (HBV) by testing positive for 1) HBV surface antigen (HBsAg+) OR 2) anti-hepatitis B core antibody positive (HBcAb+) and are HBV DNA positive

**Note:** Patients who are HBcAb+ and HBV DNA negative may be enrolled in the study. Patients who meet these criteria at screening will be identified by the central laboratory and monitored during the study as detailed in Section 8.4.10.2.

[42] Have evidence of or test positive for hepatitis C virus (HCV). A positive test for HCV is defined as: 1) positive for hepatitis C antibody (anti-HCV Ab) and 2) positive via a confirmatory test for HCV (for example, HCV-polymerase chain reaction).

[43] Have electrocardiogram (ECG) abnormalities that are considered clinically significant by the investigator and would pose an unacceptable risk to the patient if participating in the study

[44] Have contraindications to MRI (for example, claustrophobia, pacemakers, aneurysm clips, intraocular metallic fragments).

**Note:** For claustrophobia, premedication with benzodiazepine is allowed (investigator should assess for potential interactions with other concomitant medication(s) such as opiates).

**Laboratory tests are not to be repeated unless there is a technical error or clinical reason to believe a result may need to be retested, within the screening period.** Laboratory tests can be repeated a maximum of 1 time, and results must be received and reviewed by study site personnel prior to randomization. For eligibility, the most recent lab test results must not meet any of the following criteria:

[45] At screening, have a neutrophil count  $<1500$  cells/ $\mu\text{L}$  ( $<1.50 \times 10^3/\mu\text{L}$  or  $<1.50$  GI/L)

[46] At screening, have a lymphocyte count  $<800$  cells/ $\mu\text{L}$  ( $<0.80 \times 10^3/\mu\text{L}$  or  $<0.80$  GI/L)

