- s All patients will be tested for HBV at screening. Patients who are HBcAb+ at screening, regardless of HBsAb status, will have a serum HBV DNA obtained by the central laboratory. Patients who are found to be HBV DNA positive (detectable) at screening will be excluded from the trial. Patients who are HBV DNA negative (undetectable) may be enrolled into the study with required HBV DNA monitoring every 3 months during treatment and 12 weeks after the last dose of ixekizumab. If the result of the HBV DNA testing is positive, the patient must be discontinued from the study treatment and should receive appropriate follow-up medical care (refer to Section 8.4.10.2 for further information regarding the timing of discontinuation).
- t Only for females of childbearing potential. Serum pregnancy test will be done at Visit 1 only and will be performed centrally. Patients determined to be pregnant will be discontinued from treatment and will no longer be administered investigational product (see Section 7.1). Patients will undergo urine pregnancy testing at the clinic during designated scheduled visits through Week 52. Additional urine pregnancy testing can be performed at the investigator's discretion. If required per local regulations, urine testing for pregnancy may occur at intervals as required during the study treatment period and/or follow-up period.
- u For the fasting lipid profile patients are to not eat or drink anything except water for 12 hours prior to test.
- v Where collection is allowed by local regulations.
- w Only serum and plasma are collected at this visit.
- x Immunogenicity samples may also be analyzed for ixekizumab serum concentration to facilitate in the interpretation of immunogenicity data. An additional blood sample will be collected, when possible, for any patient who experiences a potential systemic allergic/hypersensitivity reaction during the study as judged by the investigator.
- y PK samples are to be collected before investigational product injection.
- z The Week 52 MRI may be collected up to 10 days **prior** to Week 52 (Visit 15).

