**Clinical Laboratory Tests**

Abbreviations: Ab = antibody; DNA = deoxyribonucleic acid; HBV = hepatitis B virus; HCV = hepatitis C virus; IgA = immunoglobulin A; RNA = ribonucleic acid; RBC = red blood cells; SGOT = serum glutamic oxaloacetic transaminase; SGPT = serum glutamic pyruvic transaminase; T4 = thyroxine; WBC = white blood cells.

- a Unscheduled blood chemistry, hematology, and urinalysis panels may be performed at the discretion of the investigator.
- b Cockcroft-Gault calculation is used for the calculated creatinine clearance.
- c For the fasting lipid profile, patients are not to eat or drink anything except water for 12 hours prior to test. Fasting is not required for the Screening Visit.
- d Serum pregnancy test for all women <60 years of age who are still of childbearing potential at Visit 1; after Visit 1, urine pregnancy test performed locally for women of childbearing potential.
- e Women  $\geq 40$  and <60 years of age who have had a cessation of menses for  $\geq 12$  months will have an FSH test confirming nonchildbearing potential ( $\geq 40$  mIU/mL).
- f Test required at Visit 1 to determine eligibility of patient for the study.
- g HBV DNA testing will be done in those patients who HBcAb+ at any time
- h See exclusion criteria (Section 5.2) specific to Hepatitis C antibody. A confirmatory test for HCV will be performed if the patient is positive for HCV antibody.
- i In countries where the QuantiFERON®-TB Gold test or T-SPOT® is available, either test may be used instead of the PPD TB test. The QuantiFERON-TB Gold test may be performed locally or centrally; the T-SPOT must be performed locally.

---

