[35] Use of any opiate analgesic at average daily doses >30 mg/day of morphine or its equivalent or use of variable doses of any opiate analgesic within 6 weeks prior to baseline randomization. For Japan patients, use of pregabalin >300 mg/day or use of variable doses of pregabalin within 2 weeks prior to baseline randomization.	Exclude from PPS if: 1. Doses >30 mg/day any time within 6 weeks before randomization; or 2. Stopped or decreased dose for a current one <7 days before randomization; or 3. Started new treatment or increased dose for current one or started a new one <6 wks before randomization	Monitor and Stats
[36] Had a live vaccination or participated in a vaccine clinical study within 12 weeks prior to Visit 2, or intend to have a live vaccination during the study or within 12 weeks of completing study treatment	Do not exclude from PPS	Monitor
[37] Had a vaccination with BCG within 12 months prior to Visit 2, or intend to have this vaccination with BCG during the study or within 12 months of completing study treatment	Do not exclude from PPS	Monitor and Stats
[38] Have a body temperature $\geq 38^{\circ}\text{C}$ (100.5°F) at Visit 2	Do not exclude from PPS	Monitor and Stats
[39] Have evidence or suspicion of active or latent TB	Do not exclude from PPS	Monitor
[40] Are positive for human immunodeficiency virus serology (HIV)	Do not exclude from PPS	Monitor and Stats

Important Protocol Deviation Category/Subcategory/Study Specific	Action for PPS Analysis	Source to Identify Protocol Deviation a
[41] Have evidence of or test positive for hepatitis B virus (HBV) and are HBV DNA positive	Do not exclude from PPS	Monitor and Stats
[42] Have evidence of or test positive for hepatitis C virus (HCV)	Do not exclude from PPS	Monitor and Stats
[43] Have ECG abnormalities that are considered clinically significant and would pose an unacceptable risk to the patient if participating in the study	Do not exclude from PPS	Monitor
[44] Patients having contraindications to MRI	Do not exclude from PPS	Monitor
[45] At Visit 1, have a neutrophil count <1.50 GI/L	Do not exclude from PPS	Monitor and Stats
[46] At Visit 1, have a lymphocyte count <0.80 GI/L; for Japan patients, lymphocyte count <1.0 GI/L	Do not exclude from PPS	Monitor and Stats
[47] At Visit 1, have a platelet count <100 GI/L	Do not exclude from PPS	Monitor and Stats

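### For a patient who is HBsAg positive, HBcAb positive and HBV DNA negative, criterion [41] excludes while its Note and Section 8.4.10.2 permit enrolment, and SAP deviation row [41] omits the HBsAg-alone route

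*Protocol*

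**What the plan says.** **Protocol 5.2, criterion [41]** excludes patients with evidence of hepatitis B, shown by "testing positive for 1) HBV surface antigen (HBsAg+) OR 2) anti-hepatitis B core antibody positive (HBcAb+) and are HBV DNA positive". The numbering makes surface antigen positivity a branch of its own and attaches the DNA condition to the core-antibody branch.

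**The Note to [41]** reads: "Patients who are HBcAb+ and HBV DNA negative may be enrolled in the study". It does not mention HBsAg, and it points the reader to 8.4.10.2 for monitoring.

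**Protocol 8.4.10.2** begins: "Patients who are HBcAb+ at screening, regardless of other hepatitis B testing results, will have a serum HBV DNA specimen obtained". It goes on to say that such patients "who are determined to be HBV DNA negative (undetectable) may be enrolled into the study", with DNA monitoring, and that patients with detectable DNA at screening are excluded.

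**Appendix 2, footnote s** states the DNA-test rule with a different qualifier: "Patients who are HBcAb+ at screening, regardless of HBsAb status, will have a serum HBV DNA obtained by the central laboratory". HBsAb is the surface antibody, not the surface antigen.

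**Appendix 3** lists HBsAg and HBcAb among the Visit 1 tests needed to decide eligibility. It limits the DNA test as follows: "HBV DNA testing will be done in those patients who HBcAb+ at any time".

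**SAP 6.16, Table RHBX.6.12, row [41]** describes the deviation as "Have evidence of or test positive for hepatitis B virus (HBV) and are HBV DNA positive". The action is to keep the patient in the per-protocol set. The source is both the monitor and statistical programming.

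**The concern.** Hepatitis B screening is an eligibility safeguard in a trial of a biologic. The protocol treats it as a safety matter: HBsAg must be known before randomization, and a later positive DNA result leads to stopping study treatment. A site that reads 8.4.10.2 or the Note on its own can find permission to enrol a patient whom the numbered criterion excludes.

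The SAP row is meant to detect patients who were enrolled against [41]. Its wording describes a narrower criterion than the numbered one, so the statistical check, if built from that wording, would not back up the monitor for the profile on which the protocol is inconsistent.

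**Working it through.** No sample-size, power or alpha figure is involved. The check sets each rule, as written, against the eight combinations of the three markers.

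Rules used:

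- Criterion [41], numbered reading: exclude if HBsAg+ or (HBcAb+ and DNA+).
- Note to [41] and the permission in 8.4.10.2: may enrol if HBcAb+ and DNA−.
- SAP row [41]: deviation if (HBsAg+ or HBcAb+) and DNA+.
- DNA test called for (8.4.10.2, footnote s, Appendix 3): if HBcAb+.

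| HBsAg | HBcAb | DNA | [41] excludes | Note and 8.4.10.2 permit | SAP row wording met | DNA test called for |
|---|---|---|---|---|---|---|
| + | + | + | yes | no | yes | yes |
| + | + | − | **yes** | **yes** | **no** | yes |
| + | − | + | yes | no | yes, but no DNA result expected | no |
| + | − | − | yes | no | no | no |
| − | + | + | yes | no | yes | yes |
| − | + | − | no | yes | no | yes |
| − | − | + | no | no | no | no |
| − | − | − | no | no | no | no |

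Results:

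1. Exactly one profile (second row) is both excluded and permitted. It also falls outside the SAP wording.
2. The permission in 8.4.10.2 is given to HBcAb+ patients only. An HBsAg+, HBcAb− patient receives no permission anywhere, so for that patient the protocol texts do not conflict. The SAP row is still deficient: the protocol calls for no DNA test, so the row's DNA condition has no result to work on.
3. For HBsAg− patients who are HBcAb+, all the places agree: DNA+ is excluded and covered by the row; DNA− is allowed and not covered.
4. Of the four HBsAg+ profiles, all are excluded by [41]. Only one (all three markers positive) meets the SAP wording with results the protocol would actually produce.

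Alternative reading of [41]: if the DNA condition is taken to govern both branches, the rule becomes (HBsAg+ or HBcAb+) and DNA+. The second row is then not excluded, and the Note, 8.4.10.2 and the SAP row agree with it. That reading goes against the numbering. It also means an HBsAg+, HBcAb− patient could not be shown to meet the criterion, because no DNA test is called for. The criterion is therefore at best ambiguous, with the SAP following one reading and the numbering supporting the other.

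Monitoring interval: 8.4.10.2 says every 3 to 4 months and footnote s says every 3 months. The HBV visits in Appendix 2 during treatment are at Weeks 0, 12, 24, 36, 44 and 52. The gaps are 12, 12, 12, 8 and 8 weeks, which satisfy both phrases.

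**The case against.** The strongest reply is that the protocol has a gate. Section 5 requires that a patient meet none of the exclusion criteria and rules out waivers. Section 8.4.10.2 is a monitoring section and does not say that it overrides 5.2. The Note to [41] can be read as the complement of branch 2 only, without reopening branch 1. Appendix 3 asks for HBsAg at Visit 1 for eligibility separately from the DNA test. On this view a careful site excludes the patient.

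This stands as the more careful reading of the protocol, but it does not remove the contradiction. Section 8.4.10.2 states eligibility in its own right, both permitting and excluding. The Note sends the reader there, and the same unqualified permission sits inside the eligibility section. A reader has to infer the order of precedence.

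On the SAP side, a reader might infer that such a patient would never be reported, or that the programmed check has no power to detect one. The documents do not support either statement. The table's footnote says a deviation is shown if either the monitor or the programming finds it, so a monitor applying [41] could list the patient. The detailed programming is in a separate specification that is not available here. The row may also be only a short label: row [42] likewise leaves out the confirmatory test in its protocol criterion. What stands is that the row, as worded, misstates the numbered criterion.

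Footnote s differs in its qualifier, but it triggers the DNA test in the same patients, so nobody is tested differently because of that phrase.

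**Conclusion.** Wrong as written, in a narrow but safety-relevant place. The protocol gives two answers for an HBsAg+, HBcAb+, DNA− patient. The SAP row does not cover an HBsAg+ patient with negative DNA, nor one who is HBcAb− and so has no DNA test. This rests on the numbered reading of [41]; on the other reading the defect is ambiguity in [41] itself, and rewording is still needed.

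The size is limited. A reader might want a head count, but the documents give neither the frequency of HBsAg positivity nor the number screened; the figure of about 300 is the number to be randomized. Few patients are likely to be affected, and no estimate can be derived.

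Efficacy results are not at risk. The ITT population is all randomized patients, and row [41] does not remove anyone from the per-protocol set. The consequence is for eligibility safety and for the completeness of deviation reporting.

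A reader might also infer that the two monitoring-interval phrases lead to different follow-up. They do not, because the scheduled visits meet both; aligning them is clerical.

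**What to change.** First, reconcile protocol 5.2 [41] and its Note, Section 8.4.10.2 and Appendix 2 footnote s so that a single rule says how an HBsAg+ patient with undetectable HBV DNA is handled. Make the two qualifiers in 8.4.10.2 and footnote s agree. Which rule is adopted is a clinical decision for the sponsor; the point here is only that every place must state the same one.

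Then reword SAP Table RHBX.6.12, row [41], to match the reconciled criterion exactly, and base the programmed check on the Visit 1 hepatitis B results. Align the monitoring-interval wording at the same time.

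The cost is text in three protocol places and one SAP table row. The rewording itself calls for no new data: HBsAg and HBcAb are already required at Visit 1, and HBV DNA is already obtained in HBcAb+ patients.
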